Invitation to Job Search Skills Workshop. The Job Search Skills Workshop will be delivered by a local consultant or organization with experience in human resources and career counseling, as well as the local employment context. The workshop will last 3 hours. The curriculum, developed by the researchers in consultation with a local HR expert, will cover the following: (30 min) introduction and review of process of job search, including identifying opportunities, building up relevant skills and qualifications, and submitting applications; (60 min) hands on tutorial on how to write an application cover letter; (15 min) break; (60 min) interview skills and practice; (15 min) presentation on local resources for career counseling and job fairs, with hand outs from these existing organizations. Other topics related to job search skills may be covered as well. The workshop will be offered either at AHRI or at a local community hall. The workshop will be held 1-3 weeks after the baseline interview and attendance of study participants will be recorded. The goal is to measure differences in uptake across treated and control arms, which will provide short-run evidence of the impact of the video on human capital investment behaviors. In order to plan for the number of attendees, we will require participants to reserve a space in the workshop. We will give them a cash payment and give them the option to keep the cash or use it to reserve a space. Participants will be randomized to receive R30 (and pay R20 to reserve) vs. R15 (and pay R5 to reserve); in both cases they will have R10 for transport. We are randomizing the incentive size in order to understand whether differences in price affect demand for the workshop, which will provide a point of comparison for the effect of the intervention video. We will be collecting data on attendance of the Job Search Skills Workshop at the individual level. Participants will reserve a spot in the workshop during the baseline survey. A workshop roster of registered attendees will be generated that contains: study ID, name, sex, date of birth, phone number, and household head name. Phone numbers will be used to remind all registered attendees 1-2 days before the workshop event. When participants arrive at the workshop, they will be asked to confirm their identity by correctly identifying one of the following: date of birth, phone number, or name household head. Attendance information will be entered into the study database and linked based on study ID. The physical attendance roster will be scanned and destroyed after data are entered. The scanned copy will be retained in a password-protected folder on the AHRI server, along with other identified operational data.

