June 2017	Registered on www.clinicaltrials.gov
August 2017	Recruitment and training of field interviewers
September – October 2017	Baseline survey and intervention
September – November 2017	Job search workshops, HIV testing vouchers
November – December 2017	Follow-up survey, home-based HIV testing

December 2017	Updated on www.clinicaltrials.gov
January – August 2018	Data extraction, quality checks, passive follow-up of HIV testing in the AHRI surveillance
September 17, 2018	Final Protocol and Pre-Analysis Plan posted to www.clinicaltrials.gov
September 18, 2018	Randomization status unblinded to researchers and posted to www.clinicaltrials.gov
March 2018 – January 2019	Analysis and preparation of manuscripts

A13. Funding and Registration

This randomized trial was jointly funded by two grants from the National Institutes of Health: 1K01MH105320 ([name]) “Economic, health, and behavioral dimensions of HIV treatment scale-up” and 1R01HD084233 ([name]/[name]) “Causal pathways to population health impact of HIV antiretroviral treatment”.

The trial is registered on www.clinicaltrials.gov as NCT03215901.

* * *

B. PRE-ANALYSIS PLAN

B1. Outcomes Variables and Definitions

B1.1 Primary Outcome Measures

Behaviors

1. Participation in HIV testing

Definition: Use of HIV testing voucher to be provided OR participation in HIV testing during surveillance household survey visit conducted at 1 to 2 months follow-up.

[Time Frame: 2 months]

2. Composite measure of future-oriented behaviors

Definition: Count variable (range 0:3) equal to the sum of the following indicators:

- Participation in HIV testing (either via the voucher or home-based testing)
- Attendance at a job search skills workshop: 1=attended
- Allocation of funds to savings tin during baseline interview: 1=participant allocated at least 50 Rand (out of 100 Rand) to the savings tin

Beliefs and Attitudes

3. Change in subjective life expectancy (at 2 months)

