We will additionally assess balance on all primary and secondary outcomes described above that are measured at baseline.

Through linkage to the AHRI surveillance, we will additionally assess balance on: whether the person has a child; household size; distance to the nearest clinic, whether anyone in the household died from HIV in the prior 10 years; whether anyone in the household is receiving public sector ART at time of baseline.

For each baseline covariate, we will report a t-test for the null hypothesis of equal means in Arm 1 vs. Arms 2+3 (pooled).

B4. Statistical analysis of treatment effects

All statistical analyses will involve comparisons across the treatment arms described above. For each outcome, we will generate the following data:

Example Results Table (fake data)

	Sample Means				Treatment Effect Estimate (95% CI)		
	Arm 1, n=XXX	Arms 2+3, n=XXX	Arm 2, n=xxx	Arm 3, n=xxx	Crude difference	Adjusted for design variables ^a	Adjusted for design, strong predictors, and baseline imbalance ^b
Outcome 1	1.2	1.5			-0.3 (-0.5 to 0.2)	-0.3 (-0.5 to 0.2)	-0.3 (-0.5 to 0.2)
			1.7		-0.5 (-0.8 to 0.0)*	-0.5 (-0.7 to 0.0)*	-0.5 (-0.7 to 0.0)*
				1.4	-0.3 (-0.5 to 0.3)	-0.3 (-0.5 to 0.2)	-0.3 (-0.5 to 0.2)
Outcome 2							
...							
Outcome k							

^aDesign variables are those variables on which balance was explicitly assessed during randomization. ^bStrong predictors of the outcome are those factors in the baseline balance table that are adjusted differences include regression adjustment for stratifying variables, variables used in the constrained randomization, and variables that were not balanced at baseline despite randomization (p-value <0.1 in F-test).

Sample means will be reported for Arm 1, the combined control (Arms 2+3), and for Arm 2 and 3 separately. When assessing changes from baseline to follow-up, we will simply define the outcomes as within-subject “differences” to facilitate comparisons with other outcomes observed only after the intervention.

Crude comparisons of outcomes between treated and comparison arms will be assessed in linear regression models, regressing the outcome on an indicator for treatment arm and indicators for week-block, a stratification variable. We will adjust our standard errors for clustering at the household level, given that error terms without households may be correlated.

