Adjusted effect estimates. We will estimate adjusted effect estimates in multivariate linear regression models. Adjustment for covariates in an RCT has three aims[23]:

- (design variables) to obtain appropriate standard errors when conducting stratified or constrained randomization;
- (strong predictors of the outcome) to reduce residual variance in the outcome, leading to smaller standard errors and narrower confidence intervals; and
- (factors with strong baseline imbalance) to eliminate the impact of any imbalances on observed baseline factors, despite randomization

(a) In our adjusted analyses, we will include the following design variables:

- Stratification variables: week block
- Constrained randomization variables: sex, age, whether the person was in school, orphan status, HIV positive status, HIV negative status (unknown is the third category), and household asset quintile

(b) We will include the following variables believed *a priori* to be strong predictors of HIV testing and human capital investment:

- Distance to nearest clinic
- Baseline subjective life expectancy
- Baseline beliefs about lifetime HIV infection risk

(c) Finally, to eliminate imbalances on observables, we will adjust for variables with $p < 0.1$ for the t-test of differences between Arm 1 and Arm 2+3.

B5. Subgroup analyses

The informational intervention is expected to have the greatest impact for individuals with low baseline survival beliefs and for individuals with high baseline beliefs about lifetime chances of contracting HIV.

Perceived likelihood of lifetime HIV infection. The impact of the informational video is likely to vary by baseline perceived risk of lifetime HIV infection. We will assess for linear effect modification of our primary outcomes by perceived lifetime infection risk.

Baseline survival expectations. The impact of the informational video is likely to vary by baseline survival expectations, with the greatest potential shift in beliefs for individuals with previously low survival expectations. We will assess for linear effect modification of our primary outcomes by baseline subjective life expectancy.

Finally, we will assess effect modification by age (continuous, 18-25) and sex of the respondent (M/F).

B6. Robustness checks

We will subject our primary results (Arm 1 vs. Arms 2+3 for primary outcomes) to robustness checks.

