Appendix C. Randomization Procedures

Variables Randomized. Study participants are randomized with respect to:

- 1) Intervention video vs. no intervention video
- 2) Pure control vs. attention placebo control (among those randomized to no intervention video)
- 3) 20 Rand vs. 5 Rand cost to reserve spot at job search skills workshop
- 4) Male-vs.-female-oriented HIV transmission questions

1. Intervention video vs. no intervention video

Level of randomization. Individuals are randomized to video intervention vs. control. Randomization is at the bounded structure level, so that all respondents within a bounded structure get the same treatment.

Stratification. Randomization is stratified by weekblock to ensure approximately equal numbers of treated and controls within weekblocks.

Constrained (restricted) randomization. The AHRI data contain robust information on baseline covariates. However, because randomization is at the level of the bounded structure, it was not possible to stratify by individual characteristics. Instead, we use a constrained (aka restricted[25]) randomization approach. For the primary analysis – comparison of intervention video vs. no intervention video, we constrained randomization to force balance on the following characteristics: sex, age, whether the person was in school, orphan status, HIV positive status, HIV negative status (unknown is the third category), and household asset quintile. We randomized the intervention treatment assignment (intervention video vs. no intervention video) 3078 times using different randomization seeds. Each time, we assessed balance on key characteristics through a t-test (i.e regression of treatment assignment on the covariate). All randomization seeds that lead to a maximum t-test value greater than 1.68 ($p<0.1$) were excluded. This excluded 62% and retained 38% of the seeds (1060 seeds). We then randomly selected two seeds from these 1060 acceptable seeds. One was used to randomize the video, the other was used to randomized the incentive for the job search skills workshop. We assessed correlation of these two interventions and re-randomized if the Chi2 p-value for the cross-tab was less than 0.5 (see tables below).

2. Pure control vs. attention placebo control (among those randomized to no intervention video)

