Within the control group – i.e. individuals assigned to “no intervention video” – we used simple randomization to assign respondents to “pure control” (no video) and to “attention placebo control” (video on another topic).

3. 20 Rand vs. 5 Rand to reserve spot at job search skills workshop

Participants were given 30 or 15 Rand and were then asked to pay 20 or 5 Rand respectively to reserve a spot in the job search skills workshop. Randomization was conducted as described above in concert with the intervention video comparison.

4. Male-vs.-female-oriented HIV transmission questions.

In the survey, respondents were asked to report on the chances that an HIV-negative woman (man) would become HIV-infected after having sex with an HIV-positive man (woman). We used simple randomization to assign respondents to the male-focused or female-focused HIV transmission questions.

Data management procedures

These random treatment assignments – video assignment, job search workshop incentive assignment, together with their AHRI internal ID numbers were submitted to the AHRI data management core, which linked them with the operational data.

Blinding

The investigators are blinded to randomization assignment throughout data collection, cleaning, and development of the analysis plan. Randomization status with respect to the intervention and placebo videos will not be revealed until after all data on the primary outcome (including uptake of testing in the 2017 AHRI surveillance) have been collected, the data have been cleaned, and final pre-analysis plan is posted.[26]

Tables. Intervention video stratified by weekblock and approximately balanced vs. Job Skills Workshop incentive

tab week TreatmentArm				
week	TreatmentArm		Total	
	C	T		
34	60	60	120	
35	60	60	120	
36	60	60	120	
37	61	59	120	
38	60	60	120	
39	60	60	120	
40	59	61	120	
41	62	58	120	
Total	482	478	960	

tab TreatmentArm JobWorkshopArm, chi2				
TreatmentA rm	JobWorkshopArm		Total	
	C	T		
C	245	237	482	
T	243	235	478	
Total	488	472	960	

Pearson chi2(1) = 0.0000 Pr = 0.998

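### The workshop price was randomised partly as a yardstick for the video effect, but Part B specifies no price analysis and B4(a) does not list price among the design variables

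*Combined protocol and SAP*

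**What the plan says.** **The factor and its purpose.** A9.4 sets two price arms: "Participants will be randomized to receive R30 (and pay R20 to reserve) vs. R15 (and pay R5 to reserve". Either way, a participant who reserves is left with R10 for transport. The section says the price is varied to learn whether it affects demand for the workshop, "which will provide a point of comparison for the effect of the intervention video".

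**How it was assigned.** Appendix C lists it third of four randomised variables: "20 Rand vs. 5 Rand cost to reserve spot at job search skills workshop". Two acceptable seeds were drawn, one for the video and one for the price. Then: "We assessed correlation of these two interventions and re-randomized if the Chi2 p-value for the cross-tab was less than 0.5". The closing table for the 960 people sampled reports "Pearson chi2(1) = 0.0000 Pr = 0.998".

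**Where it touches the outcomes.** Workshop attendance is a secondary outcome (B1.2). It is also one of the three indicators summed in the composite primary outcome (B1.1): "Attendance at a job search skills workshop: 1=attended".

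**What the models contain.** The crude model in B4 is described as "regressing the outcome on an indicator for treatment arm and indicators for week-block, a stratification variable". The adjusted model starts in B4(a) from "Stratification variables: week block" and the covariates used to constrain the randomisation. B4(b) adds three named predictors, and B4(c) adds variables that are out of balance at p < 0.1. Price is in none of these lists. It is not among the balance variables in B3, so B4(c) would not pick it up, and B5 and B6 do not mention it.

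**One text points the other way.** A footnote to the example results table in B4 defines design variables as those whose balance was explicitly checked during randomisation. The video-by-price table was checked then.

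**The concern.** Part A gives a scientific reason for a second randomisation, and the pre-analysis plan does not take it up. Part B defines no price estimate, no comparison of price with video and no interaction. A benchmark reported later would therefore be an unplanned analysis, although planning it would have taken one sentence.

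The plan is also unclear about its own adjusted model. One analyst could follow the footnote and include price, and another could follow the B4(a) list and leave it out. B4 itself gives correct standard errors under constrained randomisation as a reason to adjust for design variables, and the joint draw of video and price was one of the constraints.

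At stake are the pre-specified status of the benchmark, a small amount of precision for attendance, and very little for the composite.

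**Working it through.** **1. Reproduce the plan's figures.**
- *Video by price, 960 sampled* (Appendix C): control 245/237, treatment 243/235. Pearson chi-square = 960 × (245×235 − 237×243)² / (482×478×488×472) = 960 × (−16)² / 5.307×10¹⁰ = 0.0000046, p = 0.998. This agrees with the plan.
- *Detectable difference* (A7, target 450, taken as 225 vs 225, two-sided 5%, no clustering): (1.960 + 0.842) × √(2/225) = 0.264 SD, against the stated 0.26.

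**2. Bias in the video effect.** The share in the second price column is 235/478 = 49.163% under treatment and 237/482 = 49.170% under control, a difference of 0.007 percentage points. Multiplied by a 20-point price effect, this is 0.0014 points, which is effectively zero.

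**3. Precision for attendance.** The documents give neither a price effect *d* nor an attendance rate *p*, so both are assumed. For a 50/50 factor, R² = (d²/4) / [p(1−p)], and the standard error shrinks by the factor √(1−R²).

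| Attendance | Price effect | R² | SE reduction |
|---|---|---|---|
| 20% | 10 points | 0.0025/0.16 = 0.0156 | 0.8% |
| 20% | 20 points | 0.01/0.16 = 0.0625 | 3.2% |
| 30% | 5 points | 0.000625/0.21 = 0.0030 | 0.15% |
| 10% | 20 points | 0.01/0.09 = 0.111 | 5.7% |

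The last two rows bound the assumed range. The bottom row implies 0% attendance in one price arm and 20% in the other, so it is an extreme corner.

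**4. Precision for the composite.** Assume independent components, with testing at 10–50% and saving at 30–50%. The denominator becomes the sum of the three binomial variances.
- Attendance 20%, testing 10%, saving 30%: variance 0.16 + 0.09 + 0.21 = 0.46. R² is 0.0054 for a 10-point effect and 0.0217 for a 20-point effect, so the SE falls by 0.3% and 1.1%.
- Extreme corner (attendance 10%, price effect 20 points): variance 0.09 + 0.09 + 0.21 = 0.39, R² = 0.0256, SE down 1.3%. The detectable difference moves from 0.264 to 0.261 SD.

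**5. Chance imbalance among recruits is the same gain.** At 225 per arm, the SD of the difference in price share is √(0.25 × 2/225) = 0.0471. A 10-point price effect turns this into 0.0047 on the attendance contrast. The SE of that contrast at 20% attendance is √(2 × 0.16/225) = 0.0377. Then (0.0047/0.0377)² = 0.0156, the R² in step 3. For 20 points, (0.0094/0.0377)² = 0.0625, again identical. Imbalance and residual noise are two descriptions of one quantity.

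**6. Is the benchmark feasible?** With 225 per price arm and no clustering, 10% vs 20% attendance gives (0.10 − 1.96 × 0.03367)/0.03333 = 1.02, so power is 85%. For 10% vs 15% power is 36%. At 15% attendance each main effect has SE √(4 × 0.1275/450) = 0.0337. The difference between the video and price effects has SE 0.0337 × √2 = 0.0476, so the smallest gap detectable with 80% power is 2.80 × 0.0476 = 13 points. A video-by-price interaction has SE √(4 × 0.1275/112.5) = 0.0673, with a detectable value of 2.80 × 0.0673 = 19 points.

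**The case against.** **Scope.** The front matter presents Part B as the plan for the primary evaluation of the intervention, and the aims in A1 and the hypotheses in A4 all concern the video. A plan with that remit need not contain every analysis of an ancillary factor. This stands in part. It means the benchmark is not specified here, not that it will never be estimated. It does not remove the mismatch between the B4 footnote and the B4(a) list, which concerns the video models themselves.

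**Validity.** A reader might infer that leaving price out biases the video estimate, or leaves chance imbalance among recruits uncorrected. The documents do not support that. Price was randomised and is almost perfectly balanced across video arms in the sample. A8.3 keeps participants and interviewers blind to assignment through recruitment and consent. B3 does say that balance among those recruited is unknown, but any imbalance expected from this design is chance. At its 95% limit (1.96 × 4.71 = 9.2 points in price share), a 10- to 20-point price effect would shift the attendance estimate by 0.9 to 1.8 points. The planned confidence interval already allows for that variation: its half-width at 20% attendance is 1.96 × 3.77 = 7.4 points.

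**Strength of the price effect.** A reader might take price to be an established cause of attendance. A9.4 treats that as an open question, and no effect size is given.

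**Breadth.** A reader might want price in every outcome model. The documents suggest no route from price to HIV testing, life expectancy beliefs or attitudes. Savings are chosen out of the separate R100 compensation. Those who decline the workshop keep R30 or R15, but nothing in the documents links that to how much they save. The case is confined to attendance and the composite.

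**Conclusion.** The point holds as a minor gap in pre-specification. The price factor was randomised jointly with the video for a stated comparison that Part B does not specify. B4(a) omits it, while the B4 footnote leaves room for it.

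The video effect is unbiased with or without price. The precision forgone is small: about 0.8% to 3.2% of the standard error for attendance at 20% attendance and a 10- to 20-point price effect, and about 1.3% or less for the composite over the wider range in the working. These figures assume 225 per arm, independent individuals, equal price arms and, for the composite, independent components. The price effect and the component rates are assumptions throughout. No conclusion on the primary outcome is likely to turn on this. The main value of the change is that the benchmark becomes a planned result.

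**What to change.** - In B4(a), add the workshop price arm to the design variables for workshop attendance and for the composite, and make the table footnote agree with the list. The crude model can stay as it is.
- Pre-specify that the price coefficient on attendance, with its 95% confidence interval, is reported beside the video coefficient. State that only a large gap between the two could be detected (about 13 points at 15% attendance).
- In B3, report price arm by video arm among those recruited.
- Label any video-by-price interaction exploratory.

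The cost is one degree of freedom in two models and a few lines of text, and the variable is already in the assignment file. A12 places unblinding one day after posting, so the change should be dated before unblinding or labelled as added afterwards.
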